## 5. RISK/BENEFIT ASSESSMENT

### 5.1 *Potential Risks*

Risks of participation in this study are minimal and unlikely to occur given the safeguards in place. Psychological risks include: 1) the possibility that some participants may perceive some questionnaire or background data assessment as intrusive or causing them to feel uncomfortable; 2) breach of confidentiality. For the confidentiality protection related to audio-recording, we will store all the recordings on a password protected server. We will use a unique code number during the transcription. Once the transcription is done, all the audio recordings will be destroyed.

There is a potential risk for breach of confidentiality on WeChat. To minimize the risk, we will remind participants that they should call our study phone number for any questions related to the study participation. WeChat will only be used to send education videos. No communication will occur via WeChat. Also, we will remind them at the beginning of the study and during the bi-weekly phone calls about not sending any Protected Health Information via WeChat. In addition, our education videos do not contain any Protected Health Information and it will teach participants about diet, exercise, and stress management in general. Based on our recent completed pilot study (a similar WeChat video study in 30 Chinese immigrants), we did not observe any breach of privacy or confidentiality. All of the study team members received sufficient training on protecting privacy and confidentiality and have extensive experience in working with this hard-to-reach immigrant population. The benefits of receiving these culturally and linguistically tailored education videos outweighed the risks.

The study involves an intervention designed to enhance adherence to standard diabetes care (e.g., adherence to the prescribed diabetes medication, healthy eating, and physical activity behaviors). If our intervention improves adherence to the medication regimen or if participants make lifestyle changes (e.g., increased physical activity), more episodes of hypoglycemia may result. We will advise participants of the importance of monitoring their blood sugar as suggested by their doctors, and to contact their doctors as soon as they experience low blood sugar.

## **5.2 Benefits**

We do not anticipate that participants will receive any direct benefit from participating. However, information learned during the study may produce benefits for future patients by improving their diabetes care.

## **6. CONFIDENTIALITY**

We will use the IRB recommended RedCap for data storage (openREDCap.nyumc.org). We will also work with MCIT to set up a NYU shared network drive which is HIPAA compliant (for offsite backup storage) specifically for our study. All study personnel have already taken the mandatory HIPAA and Patient Privacy/Confidentiality training modules required by our institutional IRBs, to ensure that they are aware of the importance of patient confidentiality and all appropriate laws regarding protection against privacy breaches. Procedures will be in place to ensure that all files containing subject information will be kept in locked filing cabinets or password-protected electronic databases on a secure server. The majority of study data and all interview transcripts will be maintained in electronic files with no patient identifiers other than a study ID number; there will be one file maintained separately with its own password protection that links study ID numbers to patient identifying information.

No identifiable information about study participants will be disclosed to individuals outside those approved by the IRB to be on the study protocol. No publications that result from the study will identify individual participants.

Transcript files will also be password-protected and user-restricted. We will delete potential identifiable information from transcripts and audio/video recordings one year after the study ends. We will also encourage participants to use pseudonyms during focus groups and/or interviews. During each focus group session, the study PI will emphasize the importance of privacy and confidentiality of the discussion within the group. The text-message-based video counseling will be protected via password-enabled access. Only study participants will have access codes to open these videos. Others in the same household would not be able to open the video, unless participants choose to share the access code.

## **7. DATA ANALYSIS AND DATA MONITORING**

### **7.1 Data Analysis**

**Data analysis for Aim 1. Feasibility and acceptability:** Feasibility will be examined by calculating the percent of videos sent that are watched. We will also report the actual enrollment and retention rate. Acceptability will be examined by calculating percent of participants who report satisfaction with our intervention using a questionnaire adapted from a prior SMS intervention study.

**Data analysis for Aim 2.** We will employ the “intent to treat” (ITT) approach in analyses. We will perform a detailed descriptive analysis of all the data collected in the study. These preliminary descriptive statistics will be used to 1) check accuracy and completeness of inputted data, 2) describe univariate distribution of each variable at baseline, and 3) examine the associations between variables. We will also explore features of the data (e.g., amount and pattern of missing data, outliers, excess zeros, departures from distributional assumptions) to determine whether special techniques are needed.

**Aim 2: Proof of concept regarding the potential efficacy of the intervention for glycemic control.** We will test whether the 2 groups are comparable on baseline sociodemographic, health characteristics, and levels of acculturation. If significant differences are found, we will include the variables as covariates in the models. Between group and group by time interaction effects will be examined graphically and via linear mixed modeling for HbA1c. Calculated effect sizes will be used for sample size estimation needed for a two-sided alpha of 0.05 and power of 0.80 for the larger scale R01 study.

**Exploratory Aim: Explore the mediators of the SMS intervention.** Although underpowered, we will perform exploratory analyses of candidate mediators to evaluate the merit of further testing in a larger, adequately powered study. We will perform mediation analyses to determine whether self-efficacy and adherence to diabetes self-management explain significant variance in improvements in HbA1c.

**Focus group:** All focus groups will be audio-recorded and transcribed verbatim into Microsoft Word. Atlas will be used to store, organize, retrieve, and analyze the qualitative data. Thematic analysis will be used to analyze qualitative data. To establish coding reliability, the RA and PI will independently code up to 10% of the transcripts and identify kappa coefficient. We will meet weekly to review definitions and assignment of codes, and resolve differences through consensus. If no agreement can be made, the study team will be consulted. The RA and PI will read all transcripts and develop an open coding schema based on emergent theses. We will present coding schemes to study team, discuss emergent themes, refine codes, and develop a codebook that consists of a list of categories and topics. Once all data have been coded based on the codebook, codes most relevant to the research questions will be subject to further analysis.

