### Primary & Exploratory Outcomes

**Primary outcome: Feasibility:** Feasibility will be examined by calculating the percent of videos sent that are watched. We will also assess the feasibility by determining whether we are able to meet our recruitment goal of 30 Chinese American families and reach 80% retention rate.

**Acceptability:** Acceptability will be assessed using a satisfaction questionnaire adapted from a prior SMS intervention study.

**Secondary outcomes:** Consistent with our conceptual model (Fig. 1), we will also measure HbA1c, self-efficacy, and diabetes self-management behaviors at each time points (baseline, 3-, and 6-months). All of these scales have been used and validated in the Chinese population.

1. **HbA1c:** As part of the usual care, patients with T2D receive a HbA1c blood test at their doctors' office every 3-6 months. To minimize participants' burden, we will not conduct additional blood tests for this study. Instead, we will abstract the HbA1c testing results from the medical record at the participant's health care facility. Once we obtain the consent from participants, we will contact their doctors' offices for HbA1c results.

2. **Self-efficacy:** We will use the well-validated Stanford Diabetes Self-Efficacy Scale to measure participants' confidence to manage T2D. This instrument contains 8 items and asks participants to rate their confidence level in performing specific self-management behaviors, using 10-point Likert scale ranging from 1 (not at all confident) to 10 (totally confident).
3. **Diabetes Self-Management Behaviors:** We will administer the adapted Summary of Diabetes Self-Care Activities (SDSCA) measure to assess participants' adherence to diabetes self-management behaviors. This scale consists of 13 items and asks participants to describe their diabetes self-care activities over the past 7 days.
4. **Dietary Intake:** Informed by a previous study in Chinese Americans, we will use the adapted Mediterranean Dietary Screener to estimate dietary intake behaviors in our participants at baseline, 3- and 6-months.

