5. **Physical Activity:** We will use the International Physical Activity Questionnaire (IPAQ) short version to assess the frequency and duration of various physical activities undertaken by adults over the past 7 days. This scale will provide an estimate of the number of minutes per week participants engage in each category of physical activity (e.g., vigorous, moderate, and mild intensity).

**Covariates: Sociodemographic, health characteristics, and acculturation.** We will use a sociodemographic questionnaire to collect basic information about the participant such as age, gender, education, income, duration of residence in the US, health insurance, the diabetes medication regimen, duration of T2D, and medical history. Informed by prior literature, we will also include surveys to measure Health Beliefs, Diabetes Knowledge, Diabetes Distress, Social Support, Mental Health, the Impact of COVID-19, and memory test, which also play essential roles in diabetes management.

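### Covariates for the HbA1c model are picked by significance tests between randomised arms, and adjustment for baseline HbA1c is not pre-specified

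*Combined protocol and SAP*

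**What the plan says.** Section 7.1, Aim 2, sets out three steps. First: "We will test whether the 2 groups are comparable on baseline sociodemographic, health characteristics, and levels of acculturation". Second: "If significant differences are found, we will include the variables as covariates in the models". Third: "Between group and group by time interaction effects will be examined graphically and via linear mixed modeling for HbA1c". The level of the baseline tests is not stated, and neither effect is named as the main one. The results then go forward: "Calculated effect sizes will be used for sample size estimation needed for a two-sided alpha of 0.05 and power of 0.80" in the R01 trial.

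The candidate variables are in the covariates paragraph of section 4.3. It lists "age, gender, education, income, duration of residence in the US, health insurance, the diabetes medication regimen, duration of T2D, and medical history", names acculturation in its heading, and adds surveys of "Health Beliefs, Diabetes Knowledge, Diabetes Distress, Social Support, Mental Health, the Impact of COVID-19, and memory test". Baseline HbA1c is not on the list. Section 4.3 treats HbA1c as an outcome: "we will also measure HbA1c, self-efficacy, and diabetes self-management behaviors at each time points (baseline, 3-, and 6-months". Sections 3.3 and 4.1 use it for eligibility and for finding candidates. The text available for review contains no baseline-HbA1c covariate, no constraint of equal baseline means and no stratification by HbA1c.

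**The concern.** There are two linked faults.

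- **Selection by baseline test.** After proper randomisation, the hypothesis that the arms come from the same population is true by design. A significant result says nothing about whether the variable predicts HbA1c, and a non-significant one does not show that an imbalance is harmless. Which model is fitted therefore depends partly on chance.
- **Baseline HbA1c left out.** It is likely to be the most useful covariate, and the trial already collects it. If it is read as one of the health characteristics, it enters only after a large chance gap. If it is only the first response in the mixed model, which is the natural reading of section 4.3, the group-by-time term estimates a difference in change. That is unbiased, but usually less precise than an estimate that conditions on baseline.

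At stake is the quality of the effect size handed to the R01 sample-size calculation.

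**Working it through.** The plan states no SD, correlation, test level or detectable effect for HbA1c, so there is no figure of its own to reproduce. From the documents: 15 patients per arm (section 3.1); an 80% retention target (section 4.3), so 12 per arm; and entry at baseline HbA1c of 7% or more (section 3.3). Assumed: a 0.05 two-sided baseline test, equal population SD at each visit, and a baseline-to-follow-up correlation rho of 0.3, 0.6 or 0.8 before the entry criterion is applied.

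**1. What the test can flag (continuous variable)**

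- Threshold: t(0.975, 28) × √(2/15) = 2.048 × 0.365 = 0.748 SD.
- A realised gap of exactly 0.5 SD is flagged only if the sample SD is unusually small: P(χ²₂₈ < 28 × (0.5/0.748)²) = 0.005.
- A realised gap of at least 0.5 SD arises for any one variable with probability 2 × [1 − Φ(0.5/0.365)] = 0.17.

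**2. How often something is flagged by chance**

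Nine listed items plus acculturation make 10 candidates; the seven further surveys make 17.

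- Independent candidates: 1 − 0.95¹⁰ = 0.40 and 1 − 0.95¹⁷ = 0.58.
- Simulated with pairwise correlation 0.3: 0.35 and 0.50. With 0.5: 0.30 and 0.40.

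**3. What a flagged variable does to the HbA1c estimates**

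- *Group-by-time contrast.* Entered as main effects, flagged variables leave it unchanged with complete data. With 20–40% of follow-up values missing at random, its variance changes by at most 0.2% (simulation).
- *Between-group effect.* This one does move. In a simulation with three visits, compound symmetry, rho 0.6, 10 independent non-prognostic candidates and complete data, the rule raised its variance by about 11–12%. When something was flagged, the estimate shifted by a median of 0.10 SD.

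**4. Cost of not conditioning on baseline HbA1c**

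For one follow-up visit and n per arm, the variance of the change contrast divided by that of the baseline-adjusted estimate is

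[(1 − rho)² vx + 1 − rho²] / {(1 − rho²)[1 + 1/(2n − 4)]}

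where vx is the baseline variance left after the entry cut-off, relative to the untruncated variance. Example, rho 0.6, n = 15, vx = 1: (0.16 + 0.64)/(0.64 × 1.0385) = 1.20.

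Excess variance of the change contrast at 15 per arm:

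| Position of the 7% cut-off | vx | rho 0.3 | rho 0.6 | rho 0.8 |
|---|---|---|---|---|
| No truncation | 1 | 48% | 20% | 7% |
| 1 SD below population mean | 0.63 | 29% | 11% | 3% |
| At the mean | 0.36 | 15% | 5% | 0% |
| 0.5 SD above the mean (simulated) | – | 10% | 3% | −1% |

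Simulated figures at 12 per arm are nearly the same: 47%/20%/6%, 28%/11%/2% and 14%/3%/−1% for the first three rows.

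**5. What this means for the estimate**

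At rho 0.6 and 15 per arm the standard error is 0.326 SD for change and 0.298 SD with adjustment if there is no truncation (about 9% smaller), and 0.306 against 0.299 with the cut-off at the mean. An error above 0.20 SD then occurs in 54% of trials against 50%, or 51.5% against 50.5%.

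**The case against.** The strongest reply is that little harm follows. The selection rule is inert for the group-by-time contrast, and the difference in change is unbiased. Because patients must have HbA1c of at least 7%, some truncation is likely, so the untruncated row of the table is the least applicable. The plausible gain is then a few per cent to about 11% in variance at rho 0.6, and nil or slightly negative at rho 0.8. The study is a 30-pair pilot, HbA1c is a secondary outcome, and the R01 sample size will be very uncertain whatever model is used.

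Most of that stands, and it limits how serious the point is. It does not remove it. Section 7.1 also names a between-group effect and does not say which effect supplies the R01 figure. For that effect the rule adds variance, and the average includes the pre-treatment visit, so chance imbalance in baseline HbA1c is carried into it.

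A second reply is that the flag rates treat every candidate as continuous, whereas gender and probably insurance, medication regimen and medical history are categorical. If four or five items were tested with Fisher's exact test at a true rate of about 2%, the figures become about 30–32% for 10 candidates and 51–53% for 17. It is also not explicit that the seven surveys are among the variables tested. Both caveats are fair. A chance-selected covariate remains common either way.

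Finally, HbA1c comes from usual-care tests done every 3–6 months, so some values will be missing or old. That affects any analysis of HbA1c and is no reason to leave baseline unadjusted.

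**Conclusion.** The concern holds. The covariate rule depends on chance imbalance: it nearly always passes over a realised 0.5 SD gap, yet often admits some variable (about 30–58% of trials, depending on the number, type and correlation of candidates). It does nothing for the group-by-time contrast and, with non-prognostic candidates, adds about 11–12% to the variance of the between-group effect. Leaving baseline HbA1c unadjusted costs up to 48% in variance at rho 0.3 with no truncation, 5–20% at rho 0.6 with the cut-off at the mean or lower, and close to nothing at rho 0.8 with the cut-off at the mean.

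These sizes rest on an assumed test level, correlation and cut-off position, none of which the documents give. No bias in the difference in change and no wrong trial conclusion is claimed. Although section 2.2 labels glycaemic control a primary aim, it is framed as proof of concept. The change should be made because it is free and improves the estimate passed to the R01, but the feasibility and acceptability results do not depend on it.

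**What to change.** In section 7.1, Aim 2:

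1. Delete the baseline significance tests and the sentence that makes covariates conditional on them. Keep a descriptive baseline table by arm.
2. Always include baseline HbA1c, either as a covariate in a mixed model of the 3- and 6-month values, or by modelling all three visits with equal baseline means across arms. State which recorded HbA1c value counts as baseline.
3. Name one visit in advance, and report the adjusted between-group difference at that visit with its 95% CI as the effect size for the R01. This also settles which of the two effects now mentioned is meant.

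The cost is wording only. Baseline HbA1c is already obtained for eligibility and as an outcome, so no extra data, visits or participants are needed. The R01 sample size will still be very uncertain with 30 patients, and the confidence interval should be carried forward to show that.

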### 3. METHODS AND PROCEDURES

#### 3.1 Study Design

The proposed study is a pilot randomized controlled trial (RCT) of 6 months duration, with measurements at baseline, 3, and 6 months. Participants will be randomized to one of 2 arms (n=15 pairs each): 1) wait-list control; or 2) SMS intervention.

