#### **4.3 Study Procedures**

The proposed study is a pilot randomized controlled trial (RCT) of 6 months duration. Participants will be randomized to one of 2 arms (n=15 pairs each): 1) wait-list control; or 2) SMS intervention. The study will include 3 telephone-based measurement visits, baseline, 3, and 6 months. For patient participant, during each telephone visit, we will ask them some survey questionnaires. Once we receive their consent, we will also contact their doctors' office to obtain HbA1c results. For family/friend participant, each telephone visit will only have some survey

questionnaires. At the end of the 3-month intervention, we will randomly select 10-20 patient and family member participants to join a focus group/interview study to understand their experience with our intervention. Both patient and their family member will be paid \$30 for each measurement visit.

Upon receiving the referral list (interested patient's name and phone number) from the providers, the bilingual study staff will call the patient and provide more details about the study. If patients expressed interest in participation, the study staff will administer several screening questions over the phone. After eligibility is determined, we will ask patients to talk to their family members or friends about this study and confirmed their family/friends interests in participation. Once we received call back from patients confirming their own as well as their family members/friends' interests', we will schedule an appointment to obtain verbal consent from both and collect baseline data. The patient and family/friend pair will be randomized via a computer-generated randomization scheme with equal allocation to one of the 2 groups: 1) wait-list control; or 2) SMS.

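### The HbA1c mixed model does not name its treatment contrast or commit to baseline adjustment, so the effect size sent to the R01 calculation is undefined and could be diluted

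*Combined protocol and SAP*

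**What the plan says.** Section 2.2 makes proof of concept for glycaemic control Primary Aim 2. The outcomes part of section 4.3 lists HbA1c as a secondary outcome, measured "at each time points (baseline, 3-, and 6-months").

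For the analysis, section 7.1 says: "Between group and group by time interaction effects will be examined graphically and via linear mixed modeling for HbA1c". The next sentence reads: "Calculated effect sizes will be used for sample size estimation needed for a two-sided alpha of 0.05 and power of 0.80", for the larger R01 study.

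The covariate rule in the same paragraph covers sociodemographic variables, health characteristics and acculturation, and brings a variable in only if the arms differ significantly at baseline. Baseline HbA1c is not named as a covariate.

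Section 4.3 describes the visit at which staff "we will schedule an appointment to obtain verbal consent from both and collect baseline data" before it describes a "computer-generated randomization scheme with equal allocation to one of the 2 groups". Section 3.1 gives the size: "Participants will be randomized to one of 2 arms (n=15 pairs each").

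Five things are not stated: whether baseline HbA1c is an outcome or a covariate, whether time is categorical or linear, how the terms are coded, which visit is of main interest, and which effect and SD go to the R01 calculation.

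**The concern.** The stated use of the Aim 2 analysis is to supply an effect size for the R01, so that effect size needs a definition. A mixed model for a variable recorded at three visits, with no commitment to baseline as a covariate, is most naturally read as having all three visits in the outcome. One of those visits precedes randomisation, so its expected arm difference is zero. On that reading the between-group term is either an average that includes a structural zero or, under another common coding, the baseline difference alone. Neither is the treatment effect.

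The interaction term does carry the treatment effect. With categorical time it gives two contrasts, with linear time a slope, and the plan chooses none of these. Several different numbers could therefore be reported from the same data under the same sentence, and the choice could be made after the results are seen. The model also does not secure the precision that baseline HbA1c offers at no cost, which matters with 15 patients per arm.

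**Working it through.** The documents give no HbA1c effect, SD, correlation or R01 sample size, so there is no stated figure to reproduce. Effects, SDs and correlations below are assumptions.

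**1. What the averaged term estimates.** Let the arm differences be 0 at baseline, d3 at 3 months and d6 at 6 months. With equal weights the average over three visits is (0 + d3 + d6)/3. The post-baseline average is (d3 + d6)/2, so the ratio is always 2/3. Against the 6-month effect the loss depends on the time course:

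| Time course | Three-visit average | Loss against d6 |
|---|---|---|
| d3 = d6 | 0.67 d6 | 33% |
| d3 = d6/2 | 0.50 d6 | 50% |
| d3 = 2 × d6 | 1.00 d6 | 0% |

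**2. What the sentence permits.** One data set was simulated: 3,000 per arm, random intercept and residual SD both 0.7, true effect 0 at baseline and -0.5 at 3 and 6 months. It was fitted in several ways.

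| Model | Term | Estimate |
|---|---|---|
| Three visits, no interaction | group | -0.341 |
| Three visits, interaction, sum coding | group | -0.341 |
| Three visits, interaction, reference coding | group | -0.026 |
| Same model | group by 3 months; group by 6 months | -0.470; -0.474 |
| Three visits, linear time | group by time, per visit interval | -0.237 |
| 3 and 6 months, baseline as covariate | group | -0.485 |

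The figures agree with each other. The visit differences are -0.026, -0.026 - 0.470 = -0.496 and -0.026 - 0.474 = -0.500; their mean is -0.341.

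**3. Effect on the R01 if the averaged term were used.** For two means, n per arm = 2 × (1.96 + 0.842)² / d², with two-sided alpha 0.05 and power 0.80 from section 7.1. With d3 = d6 and the single-visit SD, d becomes 2d/3 and n is multiplied by (3/2)² = 2.25:

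| Assumed d | n per arm at d | n per arm at 2d/3 |
|---|---|---|
| 0.3 | 175 | 393 |
| 0.4 | 99 | 221 |
| 0.5 | 63 | 142 |
| 0.6 | 44 | 99 |
| 0.8 | 25 | 56 |

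If the averaged effect is instead standardised by the SD of the three-visit mean, that SD is σ√((1 + 2ρ)/3) under equal variances and equal correlation ρ. The multiplier becomes 2.25 × (1 + 2ρ)/3: 1.5 at ρ = 0.5 and 1.8 at ρ = 0.7. If a categorical-time interaction contrast is used, there is no dilution.

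**4. Precision of the undiluted options.** At one post-baseline visit, with equal variances:

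- Unadjusted interaction contrast (difference in change from baseline): variance (2/n) × 2σ²(1 - ρ).
- Baseline-adjusted contrast: variance (2/n) × σ²(1 - ρ²).
- Ratio: (1 - ρ²) / (2(1 - ρ)) = (1 + ρ)/2, which is 0.75 at ρ = 0.5 and 0.85 at ρ = 0.7.

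Estimating the slope in a small trial multiplies the adjusted variance by about 1 + 1/(N - 4). At 12 per arm (80% retention, N = 24) that is 1.05, and the ratios become 0.79 and 0.89, so a gain remains. The HbA1c entry threshold of 7% may make the baseline variance smaller than the later one. With unequal variances the large-sample difference in variance is proportional to (σ0 - ρσ1)², where σ0 and σ1 are the baseline and follow-up SDs. That is never negative, so adjustment does not lose apart from the small-sample factor.

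**5. Scale of sampling error.** For a simple two-group comparison the 95% half-width on a standardised effect is about 1.96 × √(2/n): 0.72 SD at 15 per arm and 0.80 SD at 12 per arm.

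**The case against.** A reader might infer that the plan passes an effect diluted by a third to the R01. The documents do not support that. Section 7.1 names two effects, refers to effect sizes in the plural, and never says that the between-group main effect is the one carried forward. The interaction it also names is undiluted when time is categorical. That baseline is an outcome visit is itself an inference; with baseline as a covariate the between-group effect is undiluted too. This part of the objection stands, and it limits the finding to an undefined contrast with a possible dilution.

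The sizes are conditional as well. One-third needs equal effects at 3 and 6 months, and a 12-week intervention followed to 6 months does not guarantee that. The 2.25-fold figure also needs the single-visit SD. A claim that the planned analysis has low power against an adjusted one would have to evaluate the interaction the plan names, and pilot power is not a stated goal of Aim 2.

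It can also be said that HbA1c is a secondary outcome and that sampling error of 0.72 to 0.80 SD exceeds any dilution: at an assumed d of 0.67, one-third is 0.22 SD. That is true but does not dispose of the point. Dilution is systematic and adds to the noise, and wide intervals are a reason to use baseline HbA1c. Finally, including baseline in the outcome is not an error in itself: with baseline means constrained equal across arms it is a sound model. The choice of 6 over 3 months is a design preference that the documents do not settle.

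**Conclusion.** The point holds as one of under-specification with a clearly better option available. Section 7.1 neither names the treatment contrast nor commits to adjusting for baseline HbA1c. On the natural reading, the between-group term is (d3+d6)/3 or the baseline difference, depending on coding, and neither should be used for planning.

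If the averaged term were used with d3 = d6, R01 n per arm would be inflated about 2.25-fold (single-visit SD) or 1.5- to 1.8-fold (SD of the three-visit mean, ρ of 0.5 to 0.7), relative to an unadjusted single-visit comparison. If a categorical-time interaction contrast were used, there would be no dilution. The baseline-adjusted contrast would still have about 0.75 to 0.85 of its variance, or 0.79 to 0.89 after the small-sample allowance at 12 per arm. These figures rest on assumed correlations and, for the ratios, equal variances. This is an improvement available at no data cost; the documents do not show that the R01 will be mis-sized.

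**What to change.** In section 7.1, replace the HbA1c sentence and the one after it with a specification that does the following:

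- Fit a linear mixed model to HbA1c at 3 and 6 months, with arm, categorical visit, arm-by-visit and baseline HbA1c as a covariate. Include baseline HbA1c whatever any baseline comparison shows. Equivalently, model all three visits with baseline means constrained equal across arms.
- Report the adjusted arm difference at 3 months and at 6 months, each with a 95% CI.
- Name in advance which visit's contrast, and which SD, go to the R01 calculation. Either visit is defensible; the investigators should choose before seeing outcome data.
- State that the all-visit group main effect will not be used for planning.

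The cost is a few sentences. No new data are needed: baseline HbA1c is already to be abstracted and is also an entry criterion, so a value should exist for every patient.
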